## 11.4.5.2. Other Safety

## Vital Signs

Vital signs (temperature, pulse, blood pressure, and respiration rate) will be summarized by baseline and change from baseline to each scheduled assessment time with descriptive statistics.

Number and percentage of patients with a treatment-emergent potentially clinically significant value (PCSV) will be summarized for each vital sign variable. The criteria for treatment-emergent PCSV will be defined in the SAP.

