1.4. Modifications from the Statistical Section in the Final Protocol

Only a single set of potentially clinically significant values (PCSV) tables will be provided for each applicable safety category (e.g., laboratory tests, electrocardiography, and vital signs). As the PCSV criteria defined in Section 14.3 are primarily defined in terms of changes from baseline, separate tables for patients in whom the PCSV criterion was normal or missing at baseline are not applicable.

Only listings required for the clinical study report will be produced.

In the definition of the on-treatment period for safety variables, mention of the date of patient last contact was removed; this text is not applicable as the date of patient last contact cannot be prior to the date of the last adverse event reported for an individual patient. In addition, the definition of the follow-up period for safety variables was modified to ensure a consistent reporting window for all patients.

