10.3. Vital Signs

The following vital signs parameters will be recorded and summarized according to the Schedule of Time and Events in Section 14.2:

- Systolic blood pressure
- Diastolic blood pressure
- Pulse rate
- Body temperature
- Respiratory rate
- Weight

Vital signs values and change from baseline in vital signs values at all scheduled post-baseline assessment time points will be summarized via descriptive statistics by treatment group.

For summaries of body temperature, all measurements will be converted to oral equivalent. If the method of temperature collection is not available, the measurement will not be eligible for inclusion in the summary. Measurements will be converted to oral equivalent as follows:

- axillary temperature + 0.3°C = oral equivalent temperature
- rectal temperature – 0.5°C = oral equivalent temperature
- ear temperature – 0.5°C = oral equivalent temperature

Vital signs measurements will be evaluated by PCSV criteria, specifically identifying patients with at least 1 post-baseline measurement that meets the PCSV criteria (see Section 14.3). Patients meeting the PCSV criteria will be summarized by patient count (and percentage) for a post-baseline PCSV measurement by treatment group.

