SBP	\leq 95 mmHg post-baseline and decrease from baseline by \geq 20 mmHg \geq 160 mmHg post-baseline and increase from baseline by \geq 20 mmHg	To be applied for all positions (including missing).
Temperature	Rectal, ear: $>$ 100.4 °F/38.0 °C Oral: $>$ 99.5 °F/37.5 °C Axillary or skin infrared (temporal): $>$ 99.0 °F/37.2 °C	
Weight	\geq 5% increase from baseline \geq 5% decrease from baseline	FDA Feb 2007.

[figure not shown]
ADA=American Diabetes Association; ALC=absolute lymphocyte count; ALP=alkaline phosphatase; ALT=alanine aminotransferase; AST=aspartate aminotransferase; BUN=blood urea nitrogen; CK=creatinine kinase; CPK=creatine phosphokinase; CPMP=Committee for Proprietary Medicinal Products; DBP=diastolic blood pressure; DILI=drug-induced liver injury; ECG=electrocardiography; FDA=Food and Drug Administration; Hb=hemoglobin; HR=heart rate; LLN=lower limit of normal; PCSV=potentially clinically significant value; pH=potential of hydrogen; PR=P wave, R wave; QRS=Q wave, R wave, S wave; QT=Q wave, T wave; QTcB=corrected QT interval by Bazett's formula; QTcF=corrected QT interval by Fredericia's formula; RBC=red blood cells; Ref=reference; SBP=systolic blood pressure; SGOT=serum glutamic-oxaloacetic transaminase; SGPT=serum glutamic-pyruvic transaminase; TBILI=total bilirubin; ULN=upper limit of normal; WBC=white blood cells.

[figure not shown]
14.4. [REDACTED]

[figure not shown]
[REDACTED]

[figure not shown]

[figure not shown]
14.5. [REDACTED]

[figure not shown]

[figure not shown]

Signature Page for VV-RIM-00340796 v1.0

Approval/eSignature	
---------------------	--

04-Mar-2024 18:30:56 GMT+0000

Approval/eSignature	
---------------------	--

04-Mar-2024 19:19:40 GMT+0000

Approval/eSignature	
---------------------	--

04-Mar-2024 20:08:33 GMT+0000

Approval/eSignature	
---------------------	---

04-Mar-2024 20:32:45 GMT+0000

Approval/eSignature	
---------------------	--

04-Mar-2024 22:17:03 GMT+0000

Approval/eSignature	
---------------------	--

05-Mar-2024 12:43:14 GMT+0000

Signature Page for VV-RIM-00340796 v1.0 Approved

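### Temperature is the only PCSV criterion in the SAP with no baseline condition, so its count is not limited to treatment-emergent values as the protocol asks

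*SAP*

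**What the plan says.** Protocol 11.4.5.2 (Vital Signs) states: "Number and percentage of patients with a treatment-emergent potentially clinically significant value (PCSV) will be summarized for each vital sign variable". It leaves the criteria to the SAP.

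The temperature row in SAP 14.3 reads in full: "Rectal, ear: $>$ 100.4 °F/38.0 °C Oral: $>$ 99.5 °F/37.5 °C Axillary or skin infrared (temporal): $>$ 99.0 °F/37.2 °C". It has no baseline term and no change term.

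SAP 10.3 gives the counting rule: "Vital signs measurements will be evaluated by PCSV criteria, specifically identifying patients with at least 1 post-baseline measurement that meets the PCSV criteria". The same section says "For summaries of body temperature, all measurements will be converted to oral equivalent", with these offsets:

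- "axillary temperature + 0.3°C = oral equivalent temperature"
- "rectal temperature – 0.5°C = oral equivalent temperature"
- "ear temperature – 0.5°C = oral equivalent temperature"

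SAP 1.4 explains why only one set of PCSV tables will be produced, without separate tables for patients normal or missing at baseline: "As the PCSV criteria defined in Section 14.3 are primarily defined in terms of changes from baseline".

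**The concern.** A treatment-emergent count should pick up values that become abnormal after treatment starts. The other rows of SAP 14.3 do this by requiring a normal baseline or a stated change. The temperature row does neither, so it mixes new elevations with those already present at day 1. SAP 1.4 dispenses with separate tables by baseline status because the criteria already take account of baseline, and temperature is the row where they do not.

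What is at stake is one by-arm count of raised temperature, a crude indicator of infection in a trial of an immunomodulator. With about 30 patients per arm, one patient moves the percentage by 1/30 = 3.3 points. No test, decision rule or efficacy result depends on it.

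**Working it through.** **1. Reading the table.** I read every row of SAP 14.3 (chemistry, ECG, hematology, urinalysis, vital signs) for a baseline or change-from-baseline term. Temperature alone has none. Among the vital signs:

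| Row | Form of the criterion |
|---|---|
| Systolic and diastolic pressure, pulse | post-baseline limit plus a minimum change from baseline |
| Respiratory rate | one side of the limit at baseline, the other side post-baseline |
| Weight | percentage change from baseline |
| Temperature | post-baseline limit only |

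**2. Consequence for single patients** (oral readings, limit 37.5 °C):

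| Baseline | Later | Counted now | Counted with a baseline condition |
|---|---|---|---|
| 36.6 | 37.6 | yes | yes |
| 37.6 | 37.6 | yes | no |
| 37.6 | 39.5 | yes | no |

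The second line is the defect. The third is the price of the remedy. No other SAP rule changes the second line: the PCSV convention in SAP 11.2 deals only with patients whose baseline is missing.

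**3. Do the limits clash with the oral conversion?** Oral equivalent of a limit = limit + the SAP 10.3 offset.

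- Oral: 37.5 + 0 = 37.5 °C
- Rectal and ear: 38.0 − 0.5 = 37.5 °C
- Axillary: 37.2 + 0.3 = 37.5 °C

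The Fahrenheit figures agree as well: 38.0 °C = 100.4 °F, 37.5 °C = 99.5 °F, and 37.2 °C = 98.96 °F, rounded to 99.0.

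Each of these four methods was scanned from 35.0 to 42.0 °C in steps of 0.1 °C. Raw values against their own limits and converted values against the oral limit gave the same classification at every step. Temporal readings are outside this check, because SAP 14.3 gives them a limit but SAP 10.3 gives them no offset.

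**4. Size of the baseline gap.** The documents give no temperature distribution. I assume normally distributed oral readings with mean 36.6 °C and SD 0.30 to 0.40 °C.

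P(baseline > 37.5) = 1 − Φ((37.5 − 36.6)/SD)

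| SD (°C) | z | P | Expected patients in an arm of 30 |
|---|---|---|---|
| 0.30 | 3.00 | 0.001 | 0.04 |
| 0.35 | 2.57 | 0.005 | 0.15 |
| 0.40 | 2.25 | 0.012 | 0.37 |

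Under these assumptions the figures are upper bounds on the expected miscount, because such a patient must also exceed the limit again after baseline to be counted.

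**The case against.** The strongest defence is that the protocol delegates the definition of a treatment-emergent PCSV to the SAP, and that SAP 10.3 already restricts the count to post-baseline values. On that view an absolute limit is a looser definition, not a contradiction. SAP 1.4 also says only that the criteria are primarily baseline-based, which leaves room for an exception. Its separate tables come from the protocol's laboratory section, so no temperature table promised by the protocol was lost. Delegation does allow the SAP to choose the criterion. It does not make a value that was already present and unchanged at baseline treatment-emergent, and the SAP nowhere says that temperature is meant to differ from the other rows.

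The defence is right that little is at stake. Exclusion criterion 7 removes patients with a respiratory tract infection from 4 weeks before screening up to randomization, which makes a raised baseline temperature less likely. Under Protocol 10.1.1, abnormal vital signs that are symptomatic or need corrective treatment are reported as adverse events in any case. A baseline condition also has a cost: a patient above the limit at baseline who rises further drops out of the count, as with the other rows that use a threshold at baseline.

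A reader might infer something stronger: that the oral conversion combined with method-specific limits makes the count miss rectal or ear fevers and flag normal axillary readings. That needs a converted value to be compared with the limit for its original method. Rectal or ear readings of 38.1 to 38.5 °C would then be missed, and axillary readings of 37.0 to 37.2 °C flagged. The SAP never prescribes that double correction. Once converted, a value is an oral equivalent, and only the oral limit fits it.

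**Conclusion.** The point holds as a small defect in one descriptive safety table. Temperature is the only row in SAP 14.3 without a baseline or change term, so its count can include patients whose elevation predates treatment, although the protocol asks for treatment-emergent values. The expected effect is about 0.1% to 1.2% of patients at most, conditional on the assumed mean and SD. In most realizations no patient would be affected, but a single one would shift an arm of 30 by 3.3 points.

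The documents do not support the conclusion that fevers are misclassified by thermometer type. For oral, rectal, ear and axillary readings the limits are one threshold of 37.5 °C oral equivalent expressed by method. Two details are merely unstated: whether the PCSV evaluation uses raw or converted values, which makes no difference for those four methods, and how temporal readings would be converted. The fix below settles both.

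**What to change.** Rewrite the temperature row of SAP 14.3 in the form used elsewhere in the table: at or below the limit for the method used at baseline, and above the limit for the method used post-baseline. State that it applies to raw readings. The existing limits can stay. Because each reading is judged against the limit for its own method, a change of method between visits causes no difficulty and temporal readings need no offset. The oral conversion in SAP 10.3 remains for the descriptive summaries. Patients with no baseline temperature fall under the existing convention in SAP 11.2.

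The cost is a line or two of SAP text and a minor programming change, with no new data. The accepted loss is the patient above the limit at baseline who rises further. If the SAP can no longer be amended, a table footnote and a sentence in the study report should say that the temperature count is not restricted to patients at or below the limit at baseline.
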